11 STUDY PROCEDURES

11.1 Pre-screening procedures

Study subjects will be recruited from among participating hospitals, clinics, and diagnostic centers or from general population under the responsibility of a participating Investigator. Prior to initiation of the recruitment phase, participating Investigators will identify a pool of potential study subjects. Each of these centers will identify potentially eligible patients in advance, by either reviewing past medical records and diagnoses, screening in clinics, referral from other physicians, or other sources of recruitment, to identify those aged 18 or older with clinical diagnosis of mild or moderate Atopic Dermatitis. Medical records from patient's dermatologist or primary care physician to confirm the diagnosis are optional. Verbal confirmation of the diagnosis present for ≥ 12 months is sufficient in order to fulfill this criterion.

11.2 Informed Consent Procedures

Eligible participants may only be included in the study after providing a consent using the IRB-approved informed consent. Informed consent must be obtained before conducting any study-specific procedures (i.e. all of the procedures described in the protocol). The process of obtaining informed consent should be documented in the participant's source documents. The date of signing of informed consent (and withdrawal, if later withdrawn) should be documented in the CRF.

11.3 Study Assessments

Study activities will take place according to the Time and Events table (Appendix A).

11.4 Inclusion procedures

Once all inclusion/exclusion criteria are fulfilled, the patient becomes eligible for randomization and inclusion into the treatment period. Treatment allocation will be performed as stated above in Section 8.5. Study medication will be delivered as stated in Section 8.7. Patients will be counseled on product application and diary completion.

11.5 Timing of patient's visits to the clinic

Patients will be asked to report to the clinic for their scheduled appointments. If a subject is unable to schedule an appointment within the required time frame, study staff will be asked to reschedule the patient to a day when they are able to come in within predetermined time frame.

11.6 Description by type of visit

11.6.1 Screening Visit (-21 to -14)

- informed consent completed and signed
- inclusion and exclusion criteria
- demographic data
- medical/surgical history
- perform Hanifin and Rajka criteria assessment
- current medications
- smoking status
- physical exam
- body weight
- height measurement
- obtain in clinic blood pressure and heart rate
- urine pregnancy test (for women of childbearing potential)
- Oral hygiene questions
- EASI assessment
- VAS assessment
- Skindex 16 Questionnaire
- IGA scoring assessment
- blood for clinical chemistry, serology and hematology
- Microbial content
- provide subjects with study cleanser to start using for the Washout period
- provide subjects with moisturizer to start using for the Washout period
- Start AE monitoring

11.6.2 Washout Phase (-14 to -1)

At the Screening visit once subjects become eligible for the study, they will be provided moisturizer and cleanser which need to be used for two weeks prior to the Baseline visit during the Washout phase of the study. Moisturizer use is not mandatory in the study and may be used when and as needed only. If subjects do not have the need to use the moisturizer, they may forego its use all together. However, subject will initiate the Washout phase once the chemistry and serology results become available from the lab. Once study staff receive those results, subjects will be notified by the telephone to start the Washout period phase and start using provided cleanser and moisturizer if needed. Subject will be asked to stop using their regular cleanser and regular moisturizers for two weeks prior to their Baseline visit. Subjects will also be asked to stop using bleach or vinegar baths.

- Call subjects to initiate Washout phase
- provide counseling as needed
- ask subjects to start using the provided cleanser
- as subjects to start using the provided moisturizer
- AE monitoring

11.6.3 Study Day 1-Baseline visit (-1 to 0)

- inclusion and exclusion criteria
- perform Hanifin and Rajka criteria assessment
- current medications
- obtain in clinic BP and HR
- EASI assessmentVAS assessment
- Skindex 16 questionnaire
- IGA scoring assessment
- dispense actigraphy watches and educate subjects on its use
- allocation of a randomized treatment kit number via IWRS
- delivery of the corresponding pack of Investigational Product
- obtain study medication weight for Investigational Product compliance
- first application of Investigational Product (under medical supervision)
- Microbial content
- study counseling
- study diary counseling
- replenish cleanser and moisturizer when needed
- obtain skin swabs
- blood for biomarkers
- AE monitoring

11.6.4 Week 2, 4 (Day 14, 28) study visit

- concomitant medications
- body weight

- obtain in clinic heart rate and blood pressure
- Oral hygiene questions
- EASI assessment
- VAS assessment
- Skindex 16 Questionnaire
- IGA scoring assessment
- obtain study medication weight for Investigational Product compliance
- collect study medication
- dispense investigational product to patient (Week 2)
- blood for biomarkers
- blood for clinical chemistry and hematology
- Microbial content (Week 4 visit only)
- study diary
- study counseling
- provide subjects with study cleanser and moisturizer (when necessary only)
- collect cleanser and moisturizer at Week 4 visit
- collect actigraphy watches returned by the subject at Week 4 visit
- recording of AEs if any
- skin swabs (Week 4 only)

11.6.5 Week 6 final visit (Day 42)-End of Study Visit

- record concomitant medications
- physical exam
- body weight
- obtain in clinic heart rate and blood pressure
- Oral hygiene questions
- EASI assessment
- VAS assessment
- Skindex 16 questionnaire
- IGA scoring assessment
- Skin swabs
- blood for clinical chemistry and hematology
- Blood for biomarkers
- recording of AEs if any

11.6.6 Unscheduled/Unanticipated Study visit

If an event arises that requires patient to come in to the research center, subjects should be scheduled for the Unscheduled visit and assessments are performed based on investigator discretion.

11.6.7 Early Termination Visit

Every attempt should be made to complete all visits during the defined window periods. Subjects who do not complete all required study visits and withdraw from the study before Week 6 final visit, will be asked to complete the Early Termination Visit.

During the visit, the following will be obtained:

- record concomitant medications
- · physical exam
- Body weight
- obtain in clinic heart rate and blood pressure
- Oral hygiene questions
- EASI assessment
- VAS assessment
- Skindex 6 questionnaire
- IGA scoring assessment
- skin swab samples
- obtain study medication weight for Investigational Product compliance ((if ET visit occurs before Week 4 visit)
- blood for biomarkers (if ET visit occurs before Week 4 visit)
- blood for clinical chemistry and hematology (if ET visit occurs before Week 4 visit)
- return Investigational product (if ET visit occurs before Week 4 visit)
- return cleanser and moisturizer (if ET visit occurs before Week 4 visit)
- return Actigraphy watch (if ET visit occurs before Week 4 visit)
- return study diary (if ET visit occurs before Week 4 visit)
- AE Monitoring

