13.4 Subject Withdrawal Criteria

A subject may withdraw from the study at any time at his/her own request, or may be withdrawn at any time at the discretion of the Investigator for safety, behavioral, or administrative reasons.

Reasons for withdrawal (subjects who refuse to return for any remaining study visits) or discontinuation (subjects who prematurely stop the application) at any time during the study may include, but are not limited, to the following:

- For safety reasons, either at the discretion of the Investigator or at the subject's request
- For protocol violations at the discretion of AOBiome
- Due to concomitant therapy that could interfere with the results of the study (the Investigator will report all such information on the CRFs and decide, in accordance with AOBiome, whether the subject is to be withdrawn).

All premature discontinuations and their causes must be carefully documented by the Investigator on the CRF or if needed on the AE form.

If, for any reason, a subject is withdrawn before completing the final visit, the reason for termination will be entered on the CRF. All data gathered on the subject prior to termination will be made available to AOBiome. Subjects not completing the entire study should be fully evaluated when possible. The appropriate CRFs should be completed.

If the subject chooses to withdraw before completing the study, the subject should notify the study coordinator who will instruct the subject on completion of assessments for End of Study (EOS) visit Appendix A. For

subjects who refuse to complete the assessments for their early termination, every attempt must be made to check on their status, using any mode of communication such as telephone, email, fax, or text.

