- 15. If patient's Early Termination Visit happens before Week 4, subject will be asked to return the Actigraphy watch, cleanser, moisturizer and IP to the study staff. Weigh of an IP will need to be taken.
- 16. Subjects will not need to come in to the clinic in order to start the Washout phase. Once all of the Screening procedures have been completed and subject becomes eligible for the study, supplies will be issued to the patient. However, the patient will be asked to hold off starting with

the Washout period until results of chemistry and serology become available. At that point, subject will then be notified via the phone that they may proceed with the Washout period. Start of the Washout period will be recorded in the CRF by the study staff. Subjects will be instructed to start using the provided cleanser and moisturizer if necessary.

- 17. Call to subjects to alert them to initiate the 2-week Washout phase and explain the procedures.
- 18. If patient's Early Termination Visit happens before Week 4, blood for biomarkers, clinical chemistry and skin swab will need to be collected.
- 19. Return Actigraphy watches
- 20. At Baseline, study staff will examine subject's body surface area affected by AD and will be asked to identify only one area to be sampled. Once the area is identified, study staff will sample this particular treatment area. Sampling area should be noted in subject's record, so that the same treatment area is then sampled at Week 4 visit.
- 21. Medical records from patient's dermatologist or primary care physician to confirm the diagnosis of Atopic Dermatitis are optional. Verbal confirmation of the diagnosis present for ≥ 12 months is sufficient in order to fulfill this criterion.

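### Subjects who withdraw between Week 4 and Week 6 have no scheduled off-treatment blood sample under Protocol 11.6.7 and Appendix A footnote 18, while Protocol 13.4 sends them to a visit that includes one

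*Protocol*

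**What the plan says.** Protocol 11.6.7 defines who has an Early Termination visit: subjects who "withdraw from the study before Week 6 final visit, will be asked to complete the Early Termination Visit". That covers withdrawal between Week 4 and Week 6. Physical examination, weight, blood pressure and heart rate, EASI, VAS, Skindex, IGA, skin swabs, concomitant medications and adverse events are collected whenever the visit falls. Safety labs are conditional: "blood for clinical chemistry and hematology (if ET visit occurs before Week 4 visit"). Biomarker blood carries the same condition.

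Footnote 18 to the Appendix A schedule agrees on blood but adds swabs to the condition: "If patient's Early Termination Visit happens before Week 4, blood for biomarkers, clinical chemistry and skin swab will need to be collected". The SAP repeats this footnote under its Table 1.

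Protocol 13.4 describes withdrawal differently. The subject notifies the coordinator, "who will instruct the subject on completion of assessments for End of Study (EOS) visit Appendix A". The section also states: "Subjects not completing the entire study should be fully evaluated when possible". It contains no Week 4 cut-off. In Appendix A, EOS labels the Week 6 (Day 42) column. The corresponding list in 11.6.5 includes "blood for clinical chemistry and hematology" and biomarker blood, both without condition.

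**The concern.** Labs are scheduled at Screening and Weeks 2, 4 and 6, and treatment lasts 28 days. Week 6 is therefore the only scheduled lab assessment after treatment has stopped. For a subject who leaves between Week 4 and Week 6, the Early Termination visit takes the place of that visit, yet 11.6.7 and footnote 18 omit the blood draw. Under 13.4 the same subject would have it. Two sites could each follow the protocol and collect different data.

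Safety is the primary objective, so off-treatment labs matter here even though they are only summarized descriptively. Departure in this window need not be unrelated to outcome. Protocol 8.14 makes a subject who needs rescue medication an Early Termination, so a flare after Day 28 can move a subject from a schedule with labs to one without.

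**Working it through.** This is mainly a comparison of texts. For a subject who withdraws after the Week 4 visit and before Week 6:

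| Source | Chemistry and hematology | Biomarker blood | Skin swabs |
|---|---|---|---|
| Protocol 11.6.7 | No | No | Yes |
| Appendix A footnote 18, and SAP Table 1 footnote 18 | No | No | No |
| Protocol 13.4, via the EOS column and 11.6.5 | Yes | Yes | Yes |

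Protocol 7.5 does not settle the matter, since it only refers back to Appendix A.

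**What the SAP would do with the data.** SAP 4.5.3 summarizes labs by visit. SAP 3.11 tabulates data under the visit recorded on the CRF. SAP 3.10 makes no substitution for missing values. No rule places an Early Termination lab in the Week 6 row. This already holds for labs from Early Termination visits before Week 4, which are collected.

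**How many subjects.** The inputs are 130 randomized and a 20% dropout allowance (Protocol 15.1).

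- The plan's own figure: 130 × 0.20 = 26 losses, and 130 − 26 = 104 completers. This reproduces.
- The documents do not say when the losses occur. Let f be the share of the 26 who leave between Day 28 and Day 42. The number without a scheduled off-treatment lab under 11.6.7 is 26 × f.

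| f (assumed) | 26 × f | Share of 130 |
|---|---|---|
| 0 | 0 | 0% |
| 0.10 | 2.6 | 2% |
| 14/42 (uniform over 42 days) | 8.7 | 6.7% |
| 0.50 | 13 | 10% |
| 1 | 26 | 20% |

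The loss that the wording itself causes is smaller. If a is the proportion of these leavers who would attend and give blood, the recoverable number is 26 × f × a, which is below 26 × f whenever a is less than 1.

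**Power.** The sample size rests on EASI change to Day 28: difference 3.9, SD 7.0, one-sided alpha 0.025, 52 per group. The noncentrality is 3.9 / (7.0 × √(2/52)) = 2.84, and the exact t calculation gives power 0.803, in line with the stated figure of more than 80%. Nothing in this calculation depends on late labs, and EASI is collected at every Early Termination visit.

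**The case against.** The strongest reply is that this is a small wording slip with safeguards around it. The safety endpoints in Protocol 4.1 are adverse events, and these are recorded at every Early Termination visit together with examination and vital signs. Late leavers were already scheduled for labs at Screening, Week 2 and the end of treatment. Protocol 7.5 follows ongoing, possibly related events in early terminators until resolution or for 30 days. Protocol 16.7 follows adverse events, laboratory values included, until they are normal or stable. Protocol 11.6.6 allows any assessment at an unscheduled visit. A reader might infer from 11.6.7 that late leavers have no off-treatment labs at all; these provisions show that the gap is in scheduled labs. That part of the reply stands. What the safeguards yield is selected by event and by investigator judgement, so it does not give systematic values by arm.

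The reference to EOS in 13.4 may also be a mislabel. The sentence that follows it speaks of early-termination assessments, and 7.5 points to the Early Termination column. This is plausible, but it only settles the conflict in favour of the version that omits the draw.

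A reader might further infer that the Week 4 condition is why the Day 42 lab summary covers completers only. The documents do not support this. That restriction follows from tabulation by visit and would remain if every late leaver were sampled and the result recorded under Early Termination. The accurate term is also Week 6 attendees, since Protocol 13.3 defines a completer as someone who has completed all visits.

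Finally, biomarkers and swabs are exploratory, and SAP section 5 defers the biomarker and microbial analyses. They add little weight beside the safety labs.

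**Conclusion.** The inconsistency is real, it stands in the current text, and no other section resolves it. Followed literally, 11.6.7 and footnote 18 leave subjects who withdraw after Week 4 and before Week 6 without a scheduled off-treatment chemistry, hematology or biomarker sample, and 13.4 says otherwise. The swab rule differs between 11.6.7 and footnote 18.

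The size cannot be fixed from the documents. The uniform-loss figure of about 9 is an illustration that assumes the full 20% loss occurs and is spread evenly over 42 days. As a count of samples lost through the wording, it also assumes full attendance. A reader might infer a difference between arms; unequal loss is possible, but nothing in the documents shows it. The effect is confined to descriptive safety labs and exploratory samples. It is worth correcting because safety is the primary objective and the subject is asked to attend a visit in any case.

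**What to change.** 1. In Protocol 11.6.7, remove the Week 4 condition from safety labs and from biomarker blood, so that an Early Termination visit after Week 4 collects the same blood as the Week 6 visit it replaces. The condition can stay for the return of product, watch, diary and cleanser.
2. Correct footnote 18 in Appendix A and under SAP Table 1 to match, and state one swab rule in 11.6.7 and in the footnote.
3. In Protocol 13.4, name the Early Termination visit in place of the EOS visit.
4. Add a rule to SAP 4.5.3 for summarizing these labs, for example a row by arm for the last off-treatment value, taken from the Week 6 or Early Termination visit. Without it the new samples would be collected but would not inform the post-treatment summary.

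The cost is minor wording in both documents, one additional summary row, and one blood draw per late leaver that was already scheduled for Week 6.

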12 METHODS OF ASSESSMENTS

12.1 Skin Swab Samples

Skin swab samples will be collected as Described in Appendix A. At Baseline, study staff will examine subject's body surface area affected by AD and will be asked to identify only one area to be sampled. Once the area is identified, study staff will sample this particular treatment area. Sampling area should be noted in subject's record, so that the same treatment area is then sampled at Day 28 and Day 42. Study staff will perform swabbing procedures during subject's visit. Swab samples will need to be stored in the refrigerator until shipped at the end of the study to the SciSafe Laboratories.

Swab samples may be subjected to DNA sequencing. Samples will be used for study of the skin microbial diversity and microbiome analysis While this is not our intention to study participants genome, participants sequence may be included as part of this analysis. Samples may be stored in the freezer until future research.

We will keep the specimen for up to 5 years, or until analyzed. If we complete our research and no longer need to keep the specimens, we will destroy them. Specimens will be coded and no identifiable participant information will be used. Results will not be returned to the subjects or the investigators

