	 History of being positive for Hepatitis B virus surface antigen (HBsAg) or positive Hepatitis C virus antibody (HCV Ab) at screening by laboratory testing at Screening History of renal disease Use of any investigational drugs within the previous 30 days prior to dosing or within a period of less than five times the drug's half-life, whichever is longer Use of any biologic within a period of 5 times its half-life Use of vinegar or bleach baths within 2 weeks of starting the study
DOSE REGIMEN:	Subjects will apply a total of 8 pumps of IP per application to all affected areas twice-a-day (i.e. 8 pumps in the morning and 8 pumps again at night) for 28 Days.
ASSESSMENT SCHEDULE:	All subjects will attend a screening visit not more than 21 days prior to Day 1. Subjects will be required to return to the clinic at Baseline, on Day 14 (Week 2), Day 28 (Week 4). All subjects will be asked to attend a follow-up visit 2 weeks (14 (±3) days) after the last dose of study medication.
STATISTICAL CONSIDERATIONS:	 All efficacy analyses will be performed on the ITT population and PP population The difference in treatment groups in change-from-baseline values at post-baseline visits will be analyzed using a mixed Analysis of Variance with one betweensubject variable (active group vs. vehicle group) and one within-

	subject variable One-sided two-sample equal-variance t-test will be performed as a supportive test to analyze the differences in treatment group means in change from baseline at each post-baseline visit
DURATION OF STUDY:	Subject's participation in the study will take up to 9 weeks. The estimated total study duration is 12 months. All subjects will be followed from enrollment and until the Final (End of Study Visit), which occurs 42 days following the baseline visit.

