12.12 Biomarkers

In addition to the blood drawn for the safety laboratory assessments, additional blood will be collected for the biomarker analysis at Day 1B (Baseline), Day 14, Day 28 and Day 42

Subjects must be fasting for at least 8 hours Samples will be processed on site and stored in the - 80° C Approximately 20 ml of whole blood will be drawn for biomarkers at each visit. Patients will be asked to fast for at least 8 hrs before blood for biomarkers is drawn.

Blood samples for biomarkers will be taken according to Appendix A and processed according to the lab manual. Biomarkers will be evaluated for cytokines, chemokines, inflammatory markers and immune response.

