30 APPENDIX A-SCHEDULE OF EVENTS

Visit Name	Screening	Washout phase ¹⁶	Baseline	Week 2 Day 14	Week 4 Day 28	Week 6 Final Visit (EOS) Day 42	Early Termination Visit
Visit Window in days	-21 to -14	-14 to -1	-1 to 0	+/-1	+/-1	+/-1	
Informed Consent	X						
Inclusion/Exclusion Criteria ²¹	X		X				
Demographics	X						
Medical History	X						
Hanifin and Rajka criteria	X		X				
Concomitant Medications	X		X	X	X	X	X
Smoking status	X						
Physical Exam	X					X	X
Body Weight	X			X	X	X	X
Height	X						
In office BP and HR ¹³	X		X	X	X	X	X
Urine pregnancy test for WOCBP ¹	X						
Oral Hygiene	X			X	X	X	X
EASI	X		X	X	X	X	X
VAS	X		X	X	X	X	X
Skindex 16 Questionnaire	X		X	X	X	X	X
IGA	X		X	X	X	X	X

[figure not shown]
Visit Name	Screening	Washout		Week 2	Week 4	Week 6	Early
		phase ¹⁶	Baseline	Day 14	Day 28	Final Visit	Termination Visit
						(EOS)	
						Day 42	
Visit Window in days	-21 to -14	-14 to -1	-1 to 0	+/-1	+/-1	+/-1	
Clinical chemistry ¹¹	X			X	X	X	X ¹⁸
Blood for biomarkers ¹²			_ X	X	X	X	X ¹⁸
Skin swabs			X		X	X	X ¹⁸
Microbial composition ²⁰	X		X		X		
IWRS			X				
Dispense IP to patient			X	X			
Collect Investigational Product from patient				X	X		
Investigational Product application ⁷			X	X	X		X ¹⁵
Investigational Product compliance ⁶			X	X	X		X ¹⁵
Call to subjects to initiate Washout phase ¹⁶		X ¹⁷					
Actigraphy watch ¹⁰			X		X ¹⁹		X ¹⁵
Counseling ⁴		X	X	X	X		
Study cleanser ²	X	X	X	X	X ⁹		X ¹⁵
Moisturizer ¹⁴	X	X	X	X	X ⁹		X ¹⁵
Study diary ³			X	X	X		X ¹⁵
AE monitoring ⁸	X	X	X	X	X	X	X

- 1. Urine pregnancy test for WOCBP will be done at Screening
- 2. Subjects are to be provided cleanser and moisturizer at Screening visit to start using it at the start of the Washout phase. However, cleanser, and moisturizer are available upon request in the event that subjects run out of their initial supplies.
- 3. Subjects will be asked to fill out study diary for the duration of the study (Baseline-Day 28)
- 4. Subjects will be counseled on the use of study medication, diary and answer any questions subject may have
- 5. Skin swabs will be obtained during the office visit and will be kept in the refrigerator until shipped at the end of the study

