### 1.2.3. Study Procedures

The schedule of assessments, as outlined in the study protocol, is presented in Table 1. The study flow is presented in Figure 2.

**Table 1:** Schedule of Assessments

Visit Name	Screening	Washout Phase 	Baseline	Week 2 Day 14	Week 4 Day 28	Week 6 Final Visit (EOS) Day 42	Early Temination Visit
Visit Window in Days	-21 to -14	-14 to -1	-1 to 0	+/-1	+/-1	+/-1	
Informed Consent	X						
Inclusion/Exclusion Criteria 			X				
Demographics							
Medical History							
Hanifin and Rajka criteria	X		X				
Concomitant Medications			X	X			
Smoking Status	X						
Physical Exam	X					X	X
Body Weight	X			X	X	X	X
Height	X						
In Office BP and HR 	X		X	X	X	X	X
Urine Pregnancy Test for WOCBP 	X						
Oral Hygiene	X			X	X	X	X
EASI	X		X	X	X	X	X
VAS	X		X	X	X	X	X
Skindex 16 Questionnaire	X		X	X	X	X	X
IGA	X		X	X	X	X	X
Clinical Chemistry 	X			X	X	X	X 
Blood for Biomarkers 			X	X	X	X	$X^{18}$
Skin Swabs			X		X	X	$X^{18}$
Micobial Composition 	X		X		X		
IWRS			X				
Dispense Investigational Product to Patient			X	X			

[figure not shown]
Visit Name	Screening	Washout Phase 	Baseline	Week 2 Day 14	Week 4 Day 28	Week 6 Final Visit (EOS) Day 42	Early Temination Visit
Visit Window in Days	-21 to -14	-14 to -1	-1 to 0	+/-1	+/-1	+/-1	
Collect Investigational product from Patient				X	X		
Investigational Product Application 			X	X	X		$X^{15}$
Investigational Product Compliance 			X	X	X		X 
Call to Subjects to Initiate Washout Phase 		X 					
Actigraphy Watch 			X		X 		$X^{15}$
Counseling 		X	X	X	X		
Study Cleanser 	X	X	X	X	X 		X 
Moisturizer 	X	X	X	X	X		X 
Study Diary 			X	X	X		X 
AE Monitoring 	X	X	X	X	X	X	X

Abbreviations: AE=Adverse event, BP=Blood pressure, EASI= Eczema Area and Severity Index, EOS=End of Study, IGA=Investigator Global Assessment, VAS=Visual Analog Scale, IWRS=Interactive web response system, HR=Heart rate, IP=Investigational product, WOCBP=Woman of child-bearing potential.

- 1. Urine pregnancy test for WOCBP will be done at Screening.

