- 2. Subjects are to be provided cleanser and moisturizer at Screening visit to start using it as the start of the Washout phase. However, cleanser, and moisturizer are available upon request in the event that subjects run out of their initial supplies.
- 3. Subjects will be asked to fill out study diary for the duration of the study (Baseline-Day 28).
- 4. Subjects will be counseled on the use of study medication, diary and answer any questions subject may have.
- 5. Skin swabs will be obtained during the office visit and will be kept in the refrigerator until shipped monthly to the storage lab.
- 6. Weight of an IP kit will be obtained at the at the Baseline visit. Study staff will be asked to weigh 2 bottles without the carton box PRE FIRST DOSE. Weightwill be recorded in grams. Subjects will be asked to bring both bottles back for the Week 2 and Week 4 visit. Upon return for the study visit, 2 bottles will be weighted again.
- 7. Subjects will be asked to apply the IP twice daily. First IP application will happen in the office under medical supervision.
- 8. AEs will be monitored throughout the trial, starting with the time ICF has been signed.
- 9. Cleanser and moisturizer should be returned to the study coordinator. Subjects will be asked to go back to their regular routine.

- 10. Actigraphy watch is dispensed at the Baseline visit. Subjects will be asked to wear one watch on each wrist starting at Baseline and through Day 28 visit. Subjects are allowed to take watches off during bathing/swimming/showering but will be asked to put watches back once these procedures are completed.
- 11. Patients should fast for at least 8 hours before the test. Blood for clinical chemistry will be shipped to the central lab for processing. Chemistry, Hematology, HbA1C, Lipid Panel and Angiotensin converting enzyme tests will be done at Screening, Week 2, Week 4 and Week 6. Serology will only be done at Screening. Kits will be provided by the Cenetron Labs.
- 12. Blood samples for biomarkers will be collected and processed on site within 5 minutes of collection. Patients should fast for at least 8 hours before the test. Samples will then be frozen onsite and shipped on monthly bases to the Central lab for storage.

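### The protocol holds skin swabs in a refrigerator until the end of the study and the SAP ships them monthly, so the age of a swab at shipment could range up to about 11.5 months or be capped at about 30 days

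*Protocol*

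**What the plan says.** Protocol 12.1 collects swabs from one affected area at Baseline, Day 28 and Day 42, for microbial diversity and microbiome analysis, possibly by DNA sequencing. On storage it says: "Swab samples will need to be stored in the refrigerator until shipped at the end of the study", with a named laboratory as the destination. Appendix A footnote 5 repeats the rule: "Skin swabs will be obtained during the office visit and will be kept in the refrigerator until shipped at the end of the study".

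The SAP introduces its Table 1 with the words "The schedule of assessments, as outlined in the study protocol, is presented in Table 1". Yet footnote 5 of that table says the swabs "will be kept in the refrigerator until shipped monthly to the storage lab".

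On timing, the protocol synopsis states: "The estimated total study duration is 12 months". Section 12.1 permits freezer storage of samples for future research but does not require it or say when it starts. Neither document gives a maximum refrigerated time, a swab medium or a preservative. Section 12.14 refers shipping temperature and destination to the Lab Manual.

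Biomarker blood is handled differently. Protocol 12.12 says: "Samples will be processed on site and stored in the" −80 °C. Appendix A footnote 12 has those samples frozen on site and shipped monthly to the central laboratory.

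The endpoints that the swabs serve are exploratory (Protocol 4.3): composition of the microbiome, and the difference in skin microbiota from Baseline to Day 28 between arms. SAP section 5 defers the microbial analysis.

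**The concern.** Two current documents give different shipping times for the same samples, and the protocol's version sets no limit on how long a swab may stay unfrozen. A site following the protocol literally would hold the first subjects' swabs for most of a year and the last subjects' for days or weeks.

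Two things are at stake. First, storage age becomes a source of variation unrelated to treatment. Secondly, one shipment for all of a subject's swabs makes the Baseline swab older than the Day 28 swab in every subject. If the measured flora changes at all during refrigeration, that shift is mixed with the change from Baseline that the endpoint is meant to capture. A change in a stored sample cannot be reversed later.

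**Working it through.** **Inputs.** Estimated trial duration 12 months (protocol synopsis), taken as 365.25 days, so one month is 365.25/12 = 30.4 days. Screening at Day −21 to −14 (Appendix A), so the first Baseline visit falls 14 to 21 days after the first screening. Swabs at Baseline, Day 28 and Day 42. I assume that the 12 months run from the first screening to the last Day 42 visit.

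**Check on the plan's own figure.** Subject participation: 21 + 42 = 63 days = 9.0 weeks, as the synopsis states. The 12 months is an estimate without recruitment inputs, so it cannot be re-derived.

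**Formula.** Age at shipment = shipment date − swab date.

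Oldest swabs with one shipment at trial end:
- Baseline: 365.25 − 21 = 344 days to 365.25 − 14 = 351 days
- Day 28: 28 days less, 316 to 323 days
- Day 42: 42 days less, 302 to 309 days

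| Swab | Oldest, shipped at trial end | Youngest, shipped at trial end | Shipped at own Day 42 visit | Shipped monthly |
|---|---|---|---|---|
| Baseline | 11.3 to 11.5 months | 42 days | about 42 days | 0 to about 30 days |
| Day 28 | 10.4 to 10.6 months | 14 days | about 14 days | 0 to about 30 days |
| Day 42 | 9.9 to 10.2 months | 0 days | 0 days | 0 to about 30 days |

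**Sensitivity to duration.** If the trial lasted 9 or 15 months (an assumed range), the oldest Baseline swab would be 8.3 to 8.5 or 14.3 to 14.5 months old.

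**Spread.** Assume uniform entry. With shipment at trial end, Day 28 swab age runs from 14 to about 316 days, so SD = (316.25 − 14)/√12 = 87 days. With monthly shipment, SD = 30.4/√12 = 9 days.

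**Gap between visits.** With a single shipment, Baseline age − Day 28 age = 28 days in every subject, give or take the visit windows. This holds under either reading of the protocol phrase, since 42 − 14 = 28. With monthly shipment and entry spread evenly over the shipping cycle, mean age is about 30.4/2 = 15 days at both visits, so there is no systematic gap.

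**Balance between arms.** Randomization makes the expected difference in mean age zero. With 52 per arm and SD 87 days, the standard error of that difference is 87.25 × √(2/52) = 17 days, so a chance imbalance of a few weeks is possible but not systematic.

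**The case against.** The strongest reply is that this is a stale SAP footnote. The protocol is consistent with itself in 12.1 and Appendix A. Amendment 3 records that the shipping schedule in 12.1 was updated. Other SAP footnotes also differ from the protocol: footnote 15 lists soap and shampoo where the protocol lists cleanser. An SAP does not govern specimen handling. All of this may be so, but correcting the SAP alone would confirm the longer storage rule. It would also leave open whether handling changed during the trial.

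Secondly, whether refrigeration harms these samples depends on the swab medium, which the documents do not give and the Lab Manual may. This stands: the ages can be computed, the effect on diversity cannot.

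Thirdly, *end of the study* may mean the Day 42 visit, which the protocol names the End of Study Visit. That reading is possible but less natural, since section 8.11 uses the same phrase for returning all bottles to the depot.

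Three stronger readings are tempting and not supported:
- A reader might infer that live B244 stays on active-arm swabs and alters the flora in the tube, which would bias the comparison between arms. The product is a live organism kept at 2–8 °C, applied up to Day 28 and not washed off, so some carry-over is plausible. But the documents say nothing on its viability on a swab, and the protocol's background reports no antibacterial effect in culture without ammonium.
- A reader might say that the documents prescribe different storage. Both prescribe a refrigerator; only the time of shipment differs.
- A reader might say that every other research sample must be frozen. Only biomarker blood must be. Freezing is optional for cup-scrub samples (12.13), as it is for swabs.

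**Conclusion.** The contradiction stands in current text and should be resolved. On the natural reading of the protocol, and taking the 12-month estimate at face value, age at shipment runs from 0 to about 11.5 months, against at most about 30 days under the SAP footnote. On the subject-level reading the maximum is about 6 weeks.

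Storage age is confounded with visit in any within-arm change, by about 28 days between Baseline and Day 28. If storage acts alike in both arms, that shift cancels on average in the between-arm comparison, where the main cost is noise. An arm-specific effect would need the undocumented assumption about B244 on stored swabs.

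The consequence is limited to exploratory microbiome endpoints whose analysis is deferred. Safety and EASI do not use the swabs, and S. aureus levels come from the separate cup-scrub samples. The point is modest, but cheap to act on while the microbiome analysis is still unspecified.

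**What to change.** 1. Reconcile Protocol 12.1, Appendix A footnote 5 and SAP Table 1 footnote 5 to one rule with a short, fixed refrigerated holding time, and define what *end of the study* means if the phrase is kept.
2. Preferably, freeze swabs on site at or soon after collection in the −80 °C storage already used for biomarkers, provided the swab medium in the Lab Manual allows it. Otherwise, at least ship monthly as the SAP says.
3. Record collection and freeze dates for every swab.
4. Ship or freeze the swabs now held in refrigerators, and establish which shipping rule the sites have followed.
5. Include days unfrozen as a covariate in the later microbiome analysis. This is a partial remedy: with a single shipment the Baseline-to-Day 28 gap is nearly constant within subjects, so the adjustment has to rest on age differences between subjects.

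The cost is wording in the protocol, SAP and Lab Manual, two recorded dates per swab and a few extra tubes. A separate monthly shipment may also be needed, because swabs go to a named laboratory that the documents do not identify with the central laboratory receiving the biomarker samples.
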